### **6.1.4. Treatment-related TEAEs**

The following TEAEs will be summarized by relationship to study treatment:

- TEAEs by SOC, PT, and relationship
- Grade 3 or 4 TEAEs by SOC, PT and relationship

### **6.1.5. Serious TEAEs**

The incidence of serious TEAEs will be summarized as below:

- Serious TEAEs by SOC and PT
- Serious TEAEs by SOC, PT and relationship to study treatment
- Most commonly reported ( $\geq 2\%$ ) serious TEAEs by SOC and PT

A similar summary of serious TEAEs will be presented by SOC, PT and study week.

In addition, a listing of serious TEAEs will be provided.

### **6.1.6. TEAEs Leading to Treatment Discontinuation**

The TEAEs leading to permanent treatment discontinuation will be summarized by SOC, PT and grade 3/4 for those subjects indicated as having discontinued study treatment due to an adverse event on the eCRF “End of Treatment” page.

A listing for subjects who discontinued study treatment due to AE will be provided.

### **6.1.7. TEAEs Leading to Dose Modification**

Incidence of TEAEs leading to dose modification (delay within cycle, cycle delay, or dose skipped) will be summarized by SOC, PT and grade 3/4 for each treatment.

### **6.1.8. TEAEs with Fatal Outcome**

The TEAEs with fatal outcome will be summarized by PT and relationship to study treatment for each treatment group. A listing of TEAEs with fatal outcome will also be provided.

### **6.2. Deaths**

The number of subjects who died during the study and the primary causes of death will be summarized for the ITT analysis set. In addition, the similar summaries will be presented for all deaths and death within 30 days of last dose or active monitoring completion respectively.

A listing of subjects who died during the study will be provided.

### **6.3. Adverse Events of Clinical Interest**

#### **6.3.1. Summary of Infusion/Injection-related Reactions (IRR)**

The incidence of infusion/injection-related reactions (IRRs), as recorded on eCRF, will be presented by SOC, PT, and toxicity grade 3/4. In addition, the total number of subjects with IRR in more than 1 infusion/injection will be presented. The timing of IRR will also be evaluated through a summary of IRR by event onset time.

A listing of infusion/injection-related reactions will be provided.

#### **6.3.2. Injection-site Reactions**

For the Dara-SC treatment group, injection-site reactions will be recorded on eCRF. The incidence of injection-site reactions will be summarized by SOC, PT, and toxicity grade 3/4. A listing of injection-site reactions will be provided.

#### **6.3.3. Infections and Infestations**

Infections and infestations refer to the adverse events with SOC of infections and infestations. The grade 3 or 4 treatment-emergent infections and infestations will be summarized by preferred term and relationship to treatment.

#### **6.3.4. Hemorrhage Events**

Hemorrhage events refer to the adverse events defined by Standardized MedDRA Queries (SMQ) with the first subcategory SMQ of hemorrhage terms (exclude laboratory terms). Incidences will be summarized by MedDRA system-organ class and preferred term. The summaries will be presented by all grades and maximum toxicity grade for each treatment group.

#### **6.3.5. Second Primary Malignancies**

A listing of subjects who reported second primary malignancies during the study will be provided. This listing will include diagnosis, study day of diagnosis, recurrence of a prior existing malignancy (yes, no) and pathology diagnosis (biopsy, aspirate etc.) information whenever a second primary malignancy is observed. In addition, treatment related to second

primary malignancy, cumulative study treatment exposure, and whether or not subjects received subsequent anti-cancer therapy (yes, no) information will also be presented in the listing.

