	Notes	Active Monitoring (Arm A; 12-week disease evaluations) / Treatment Phase (Arm B; 4-week treatment cycles after Cycle 6) ^a (up to 39 cycles or 36 months, whichever occurs first)						End of Active Monitoring/ End of Treatment	Pre-PD Follow-up	PD	Post-PD Follow-up	
		Screening (within 35 days before randomization)	C1-2		C3-6		C7-39					
		D1 ^b	D8	D15	D22	D1	D15	D1	30 (±3) days after the last Daratumumab dose ^c	every 12 weeks (±7 days)	at least every 6 months (until end of study)	
		Daratumumab (Arm B): Continuous from the time of signing of ICF until 30 days after last daratumumab dose, or until start of next therapy, whichever is earlier.										
Survival, Second primary malignancies		Throughout study until the end of study, and at a frequency of at least every 12 weeks until PD.										X
Best response to first-line MM treatment, PFS2	Investigator review; no central laboratory testing											X
Biomarkers Assessments. Per Amendment 6 all biomarker assessments by central lab are discontinued. FISH testing at PD to be performed locally.												
Whole blood (biomarkers)	Cytometry by time of flight	X	Week 24, Week 48, Week 96, and at suspected CR (±1 month with disease evaluations)					X		X		
	PBMCs	X										
	Plasma	X	Every 12 months from C1D1 (±1 month with disease evaluations)							X		
Stool (biomarkers)	Microbiome	X	Week 24 and at suspected CR (±1 month with disease evaluations)							X		
Bone Marrow aspirate ^m	Cytogenetics by FISH ^k	X								X		

Notes	Active Monitoring (Arm A; 12-week disease evaluations) / Treatment Phase (Arm B; 4-week treatment cycles after Cycle 6) ^a (up to 39 cycles or 36 months, whichever occurs first)						End of Active Monitoring/ End of Treatment	Pre-PD Follow-up	PD	Post-PD Follow-up
	Screening (within 35 days before randomization)	C1-2		C3-6		C7-39				
		D1 ^b	D8	D15	D22	D1	D15	D1		

- a. Treatment Phase (Arm B): daratumumab SC administered weekly in Cycles 1 and 2, every 2 weeks for Cycles 3 to 6, and every 4 weeks thereafter until 39 cycles or 36 months (whichever occurs first) or confirmed PD.
- b. C1D1 should occur within 5 days after randomization (Arm B).

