9.1.4. Follow-Up Phase

The Follow-up Phase will begin once the subject completes 39 cycles or 36 months (whichever occurs first) of active monitoring (Arm A) or daratumumab treatment (Arm B). Reasons for premature discontinuation of active monitoring or daratumumab treatment are listed in Section 10.2. Subjects who discontinue before PD must continue to have disease evaluations as described in Section 9.2, until study completion or confirmed PD (or other reasons as outlined in Section 10). If subjects have not progressed to MM, then no other treatment for SMM or MM is allowed during the study. Follow-up for first-line MM treatment (including the response to first-line MM treatment), second primary malignancies, and survival status will be obtained as specified in the Time and Events Schedule (Table 1). Survival will be followed until the end of the study and at a frequency of at least every 12 weeks until PD. After PD, survival is to be followed at least every 6 months, until the end of the study.

If PRO or survival information is obtained via telephone contact, then written documentation of the communication must be available for review in the source documents. If the subject has died, then the date and cause of death will be collected and documented in the eCRF.

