10.2. Discontinuation of Active Monitoring (Arm A) or Study Treatment (Arm B)

Discontinuation of Active Monitoring (Arm A) or Study Treatment (Arm B)

A subject will not be automatically withdrawn from the study if he or she has to discontinue active monitoring or treatment before the end of the Active Monitoring or Treatment Phase. The End-of-Active Monitoring/End-of-Treatment Visit and Follow-up Visit assessments should continue as specified in the Time and Events Schedule ([Table 1](#)).

A subject must be discontinued from active monitoring or daratumumab treatment if:

- The investigator believes that for safety reasons or tolerability reasons (eg, adverse event) it is in the best interest of the subject to discontinue study treatment
- A subject randomized to Arm B becomes pregnant unless the subject (or the subject's legally acceptable representative), investigator, and sponsor agree the benefits outweigh the risks to the fetus and continuation of study treatment is in the best interest of the subject. A subject randomized to Arm A who becomes pregnant may remain on the study (refer to Section 4.3). For a pregnant subject who remains on the study, any study procedures deemed by the investigator to be potentially harmful to the fetus (eg, CT scans) may be deferred until the subject is no longer pregnant.
- The subject (or the subject's legally acceptable representative) withdraws consent for administration of study treatment
- The subject experiences unacceptable toxicity, including IRRs described in Section 6.4
- The subject's daratumumab dose is held for more than 28 days due to treatment-related adverse events (Arm B only)
- The subject experiences disease progression (definition see Section 9.2.2). [Biochemical progression without meeting IMWG diagnostic criteria for MM requiring therapy ([Table 9](#)) does not constitute a reason for discontinuation of therapy.]
- A subject who experiences a second primary malignancy that cannot be treated by surgery alone must be withdrawn from the study. However, a subject who develops a malignancy that may be cured surgically may continue to receive active monitoring (Arm A) or the assigned

study treatment (Arm B) and should continue to be followed for subsequent progression of MM.

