12.3. Procedures**12.3.1. All Adverse Events**

All adverse events and special reporting situations, whether serious or non-serious, will be reported as specified in the Time and Events Schedule. Beyond the adverse event reporting period, only adverse events that are considered to be possibly, probably, or very likely related to study drug need to be reported.

The sponsor will evaluate any safety information that is spontaneously reported by an investigator beyond the time frame specified in the protocol. Disease progression should not be recorded as an adverse event or serious adverse event term; instead, signs and symptoms of clinical sequelae

resulting from disease progression/lack of efficacy will be reported if they fulfill the serious adverse event definition (refer to Section 12.1.1). For adverse events that result in death, death should be recorded as an outcome of the adverse event and should not be recorded as an adverse event or serious adverse event. The adverse event that resulted in the death should be reported as a serious adverse event. All events that meet the definition of a serious adverse event will be reported as serious adverse events, regardless of whether they are protocol-specific assessments.

All adverse events, regardless of seriousness, severity, or presumed relationship to study drug, must be recorded using medical terminology in the source document and the eCRF. Whenever possible, diagnoses should be given when signs and symptoms are due to a common etiology (eg, cough, runny nose, sneezing, sore throat, and head congestion should be reported as "upper respiratory infection"). Investigators must record in the eCRF their opinion concerning the relationship of the adverse event to study therapy. All measures required for adverse event management must be recorded in the source document and reported according to sponsor instructions.

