### **6.1. Adverse Events**

AEs will be recorded in standard medical terminology and graded according to the National Cancer Institute Common Terminology Criteria for Adverse Events (NCI-CTCAE), Version 4.03. For AE reporting, the verbatim term used in the CRF by investigators to identify adverse events will be

coded using the latest version of Medical Dictionary for Regulatory Activities (MedDRA) coding dictionary.

The relationships to study medication will be recorded as not related, doubtful, possible, probable, or very likely on eCRF for all the AEs. Adverse events will be categorized and summarized according to their highest relationship to study medication. An adverse event is considered as related to study medication if the relationship is recorded as possible, probable or very likely.

For subjects treated with daratumumab, treatment-emergent adverse events (TEAEs) are defined as any AE with onset date and time on or after that of the first dose through 30 days after the last study drug administration, or the day prior to start of subsequent therapy, whichever is earlier; or the follow-up AE (linked to an existing TEAE) with onset date and time beyond 30 days after the last study agent administration but prior to the start of subsequent therapy; or any AE that is considered related to (very likely, probably, or possibly related) study medication regardless of the start date of the event. AEs with missing or partial onset date and time will be considered as treatment-emergent unless the onset date and time of an AE can be determined as earlier than that of the first dose, or later than 30 days after last study drug administration. For subjects on active monitoring, treatment-emergent adverse events will be defined as AEs that occur after randomization and prior to start of subsequent therapy, or prior to discontinuation from the study or if the subject continues on study for 3 years, then up to 30 days after that, whichever is earlier.

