### 2.2. Duration of exposure: censored & non-censored

The incidence rate for a patient is derived from the duration of exposure to treatment of that patient. When averaging incidence rates, a patient's duration of exposure is given either A) by the time when the event has occurred (non-censored data), or B) by the total duration of treatment in case the patient does not show the adverse event in question (censored data). Depending on whether a patient has an adverse event or not, the duration of exposure enters the denominator in its non-censored or censored form, respectively.

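### Second primary malignancies are collected in both arms to the end of the study, but the SAP plans only a listing of them and no by-arm incidence over full follow-up

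*SAP*

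**What the plan says.** **Collection.** In Protocol Table 1, survival and SPMs share one row with no arm restriction: "Throughout study until the end of study, and at a frequency of at least every 12 weeks until PD". The row is also marked for follow-up after progression. Protocol 9.1.4 confirms that "second primary malignancies, and survival status will be obtained as specified in the Time and Events Schedule".

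**Analysis.** SAP 6.3.5 says "A listing of subjects who reported second primary malignancies during the study will be provided". The listing carries diagnosis, study day, recurrence, pathology, treatment of the SPM, cumulative exposure and subsequent therapy. No count, percentage, rate or interval by arm is specified. The other four events of clinical interest in SAP 6.3 all get summaries.

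**Treatment-emergent window (SAP 6.1).** For daratumumab it closes 30 days after the last dose or just before subsequent therapy, but it readmits "any AE that is considered related to (very likely, probably, or possibly related) study medication regardless of the start date of the event". For the other arm, "For subjects on active monitoring, treatment-emergent adverse events will be defined as AEs that occur after randomization and prior to start of subsequent therapy", with further limits at study discontinuation and at three years plus 30 days. That arm has no rule for late related events.

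**Reporting after the window.** Under Protocol 12.3.1, "only adverse events that are considered to be possibly, probably, or very likely related to study drug need to be reported".

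**Withdrawal.** Protocol 10.2 adds: "A subject who experiences a second primary malignancy that cannot be treated by surgery alone must be withdrawn from the study".

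**The concern.** Subjects are asymptomatic, and a new malignancy is the kind of harm that can appear late. The protocol follows it to study end in both arms; among the events in SAP 6.3 it is the only one scheduled for collection that long regardless of relatedness. Yet the planned output does not use the follow-up as a comparison. From the listing a reader could count cases per arm, but would have no time at risk and no interval. The treatment-emergent tables cannot substitute, because their late-event rule applies to one arm only.

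The end-of-study data go into an addendum to the study report (Protocol 3.1), and neither document specifies an SPM analysis for it.

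**Working it through.** **Step 1. Where could an SPM be summarised by arm?** (A = active monitoring, B = daratumumab)

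| Output | SPMs it shows | SPMs it misses |
|---|---|---|
| TEAE tables (SAP 6.1.2) | Reported as adverse events inside the window; in B also late related or linked events | Other late SPMs |
| Exposure-adjusted rates (SAP Attachment 1) | The same TEAEs; time at risk is treatment: "The incidence rate for a patient is derived from the duration of exposure to treatment of that patient" | Other late SPMs; person-time after treatment |
| Deaths (SAP 6.2) | Fatal, if recorded as the primary cause | All non-fatal |
| Disposition (SAP 4.2) | Study discontinuations by reported reason | SPM is not a separate withdrawal reason in Protocol 10.3 |
| Listing (SAP 6.3.5) | All | No denominator or rate |

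Late non-fatal SPMs in A, and late non-fatal unrelated SPMs in B, have no assured route into a by-arm summary.

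**Step 2. How much follow-up is late?**

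Inputs from Protocol 11.2: 180 per arm, 24-month accrual, median OS 100 (A) and 125 (B) months. The primary cutoff is month 24 + 24 = 48. Study end is 8 years = month 96 (Protocol 17.9.1). The longest ordinary window is 36 months + 30 days, about 37 months (SAP 6.1). The documents give no dropout rate, so 0%, 5% and 10% a year are assumed.

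Let λ = ln 2 / median OS, δ = −ln(1 − annual dropout)/12 and k = λ + δ. A subject entering at month a has F = T − a months available to cutoff T.

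- Person-years per arm = (180/12) × average over a in (0, 24) of (1 − e^(−kF))/k.
- Part inside 37 months: replace F by min(F, 37).
- Expected deaths per arm = 180 × average of (λ/k)(1 − e^(−kF)).

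*Check against the plan's OS counts.* The plan expects 64 deaths at the primary analysis and 107 at study end. With no dropout the formula gives 72 and 146; with 10% a year, 61.9 and 106.7. Matching the plan exactly needs 7.8% (for 64) or 9.9% (for 107). Ten percent is therefore a reasonable working case, with zero as the other bound.

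*Worked case: A, month 96, no dropout.* λ = 0.6931/100 = 0.006931.
- Average of e^(−λF) = (e^(−72λ) − e^(−96λ))/(24λ) = (0.6071 − 0.5141)/0.1664 = 0.559.
- Full follow-up: 15 × (1 − 0.559)/0.006931 ≈ 954 person-years.
- Inside 37 months: 15 × (1 − 0.7738)/0.006931 ≈ 490.
- Beyond: 464, or 48.7%.

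| Cutoff | Dropout per year | Person-years A / B | Beyond month 37, A / B |
|---|---|---|---|
| Month 48 | 0% | 476 / 488 | 6.0% / 6.2% |
| Month 48 | 10% | 409 / 419 | 4.9% / 5.0% |
| Month 96 | 0% | 954 / 1,006 | 464 / 504 (48.7% / 50.1%) |
| Month 96 | 5% | 815 / 857 | 360 / 391 (44.2% / 45.7%) |
| Month 96 | 10% | 698 / 731 | 277 / 300 (39.7% / 41.1%) |

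**Step 3. How many SPMs is that?** The documents give no SPM rate. Assume 0.5 to 2 per 100 person-years; the expected number is rate × person-years / 100.
- Month 48: about 20 to 30 person-years per arm lie beyond month 37, so 0.1 to 0.6 SPMs.
- Month 96, 10% dropout: A 1.4 to 5.5, B 1.5 to 6.0.
- Month 96, no dropout: A 2.3 to 9.3, B 2.5 to 10.1.

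Some of these would still be tabulated, as related in B or as fatal in either arm.

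**Step 4. What would the added rate look like?** Take 7 first SPMs in 698 person-years: 7/698 = 1.0 per 100. The exact 95% limits are χ²(0.025; 14)/(2 × 698) = 0.40 and χ²(0.975; 16)/(2 × 698) = 2.07 per 100.

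**The case against.** **This is a preference.** No objective, endpoint or hypothesis names SPMs. A detailed listing is an accepted way to report rare events, and Protocol 11.10 allows listings and narratives. Case counts by arm can be read from it. A person-year rate also goes beyond what SAP 6.3 gives the other events of interest. All of this stands and sets the severity. It does not supply a denominator or a symmetric comparison.

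**Late serious SPMs may be reported anyway.** Protocol 12.3.2 asks for every serious adverse event during the study, and Protocol 11.10 includes all reported events by arm. Many malignancies would be serious. But Protocol 12.3.1 limits reporting after the window to related events, whether serious or not. The two texts pull in different directions. A reader might infer that late SPMs can never reach an adverse event table; the documents do not support that. They do not assure that such SPMs will reach one either.

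**SPM is not the only event reported late.** Related infections or hemorrhages can also be reported after the window. What sets SPM apart is scheduled collection to study end regardless of relatedness.

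**Progression does not itself close the window.** A reader might assume it does and arrive at a larger uncovered share. SAP 6.1 closes the Arm A window at subsequent therapy, study discontinuation or three years plus 30 days. Any such calculation must also let deaths count once only, since PFS includes death. The month-37 shares above do not depend on PFS.

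**The overall rate is hard to interpret.** Myeloma therapy after progression is not randomised. This stands, and it is why the pre-therapy version matters more.

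**Conclusion.** The point holds as a reporting gap of the lowest severity. Following the plan gives no symmetric by-arm SPM incidence over full follow-up. At the primary cutoff, which Protocol Amendment 6 describes as already passed, the effect is negligible: 5-6% of person-years and less than one expected SPM per arm beyond month 37. At study end about 40% to 50% of person-years lie there.

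These shares rest on the plan's OS medians, uniform accrual and an assumed dropout of 0% to 10% a year. The case numbers rest further on an assumed SPM rate. Earlier closure of the window, through stopped treatment or subsequent therapy, would raise the uncovered share by an amount the documents do not let one estimate.

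Three stronger readings should be resisted. The plan is not silent on SPMs by arm, since early, related (in B) and fatal cases are partly covered. Nothing shows that the gap favours one arm: which arm loses more follow-up depends on how often daratumumab is stopped early. And neither the data nor the PFS analysis is harmed.

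**What to change.** Add to SAP 6.3.5, on the safety set and by arm:

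- number and percentage of subjects with a first SPM;
- rate per 100 person-years with exact 95% confidence interval, with time at risk from first dose (B) or randomisation (A) to first SPM, death or last contact;
- two versions: follow-up before the start of subsequent anti-myeloma therapy, which is the one that speaks to daratumumab, and all follow-up;
- timing: the end-of-study cutoff. Keep the listing.

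The cost is a few lines of text and one table. Diagnosis day is already a listing field, SAP 2.7.4 handles partial start dates of subsequent therapy, and SAP 5.3.6.1 derives the last-known-alive date. That date should be cut at withdrawal from the study, because survival may be updated later from public records when SPM status is not. Counting only the first SPM means the withdrawal rule in Protocol 10.2 does not shorten time at risk.

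The drawbacks are few events, wide intervals as in step 4, and an overall rate mixed with the effects of later myeloma therapy.

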### 6.3.6. Adverse Events by Subgroups

The subgroup analysis for the following TEAEs will be performed based on the subgroups specified in Section 2.4:

- Overview of TEAEs
- Summary of all TEAEs
- Grade 3 or 4 TEAEs
- Serious TEAEs

